6.6.1 Dose Modifications Based on Haematological Parameters

Myelosuppression and cytopenias are expected outcomes of leukaemia treatment, hence the aim of these dose modification guidelines is to prevent cumulative bone marrow suppression. Dose modifications for haematological changes are not allowed in the first 35 days after starting AZD0466 during Cycle 1 but supportive care should be provided as clinically indicated.

If a patient experiences a clinically significant and/or **unacceptable haematological toxicity** (including a DLT) considered by the Investigator to be related to study treatment and not attributable to the disease (or to disease-related processes) under investigation, dosing in subsequent cycles will be withheld and may subsequently be restarted at **one lower dose** (equivalent to one dose reduction; [Figure 3](#)) and supportive therapy ([Appendix F](#)) administered as required. Recommended dose modifications for haematological toxicities associated with AZD0466 observed in patients with haematological malignancies are shown in [Table 5](#).

Table 5 Recommended Dose Modifications for Haematological Toxicities

Toxicity Grade	Occurrence	Action
Grade 4 neutropenia, with or without fever or infection	Occurrence prior to achieving remission	Administer prophylactic or treatment anti-infectives and growth factor support as clinically indicated. In most instances, AZD0466 should not be interrupted due to neutropenias prior to achieving remission; however, Investigator judgment may be applied to determine the aetiology of neutropenias.
	Occurrences after achieving remission and lasting at least 7 days	Withhold AZD0466 until infection is resolved, and antibiotics no longer required (except prophylactic) and ANC $\geq 0.5 \times 10^9/L$. ^a Dosing should be discussed with Medical Monitor.
Presence of significant bleeding events with or without thrombocytopenia, such as: 
• Grade 3 or 4 haemorrhage• Any grade serious haemorrhage event• Any grade intracranial haemorrhage or haematoma	Any	Withhold AZD0466 Maintain platelets at $\geq 50 \times 10^9/L$ until resolution of bleeding. Following discussion with Medical Monitor, if evidence of clinical benefit, may consider re-challenge at 2 dose levels below current dose.

Table 5 Recommended Dose Modifications for Haematological Toxicities

Toxicity Grade	Occurrence	Action

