	< 0.5	< 50	< 5% blast and cellularity < 10%	
 No count recovery at day 35 hold AZD0466 wait to see if recovery at Day 42. If no recovery, repeat bone marrow at Day 42. Blasts count < 5% and no count recovery this is prolonged myelosuppression and a DLT. Discontinue AZD0466 Blasts count \geq 5% and no count recovery, either continue to Cycle 2 or discontinue due to lack of response after discussion with Medical Monitor
	< 0.5	< 50	> 5% blast	
 If significant reduction of leukaemic burden and clinical benefit as assessed by the Investigator, discuss with the Medical Monitor and may continue to Cycle 2. If lack of clinical response or benefit consider discontinuation from study.
Cycle 2 and beyond	> 0.5	> 50	< 5% blast and normal cellularity (> 10 %)	
 Continue to next cycle
			<5% blast and bone marrow hypocellular (< 10% cellularity)	
 Hold AZD0466 and monitor for count recovery and assess bone marrow weekly. Once adequate hemopoiesis met (> 20% cellularity) restart AZ0466. Consider restarting at one lower dose than the current dose.
	> 0.5	> 50	> 5% blast	
 Continue to next cycle if the patient is deriving benefit in the opinion of the Investigator
	< 0.5	< 50	Aplastic/ Hypoplastic (< 10% cellularity) and < 5% blasts	
 Hold and monitor for count recovery and assess bone marrow weekly. Once adequate hemopoiesis met (> 10% cellularity), restart AZ0466. Consider restarting at one lower dose than the current dose. If hypocellularity is due to high leukaemic burden (95% blast) or if Investigator attributes hypocellularity to residual leukaemia, consider dosing after discussion with Medical Monitor

Table 6 Treatment Criteria Based on Bone Marrow, ANC and Transfusion Independent Platelet Count in the Absence of Peripheral Blasts

Event	ANC ($10^9/L$)	Platelets ($10^9/L$)	Bone marrow	Action
	< 0.5	< 50	> 5% blast	
 Discuss with Medical Monitor consider discontinuation due to continued lack of response. Further cycles may be considered

ANC, absolute neutrophil count; DLT, dose-limiting toxicity.

Contact the Medical Monitor to discuss action with AZD0466 for any scenario not described above.

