11.4.7 Dose-limiting Toxicity

11.4.7.1 Definition of DLT-evaluable Patients

A DLT-evaluable patient is defined as a patient that has received AZD0466 in Part A and either:

- Has completed the 35-day DLT evaluation period in Cycle 1 and has received at least 75% (3 doses at target dose from Day 8 to Day 29) of the total amount of the planned dose of AZD0466

Or

- Has experienced a DLT during the 35-day DLT evaluation period in Cycle 1.

Patients who have not had a DLT but do not complete the 35-day DLT evaluation period may be replaced to achieve the required minimum number of DLT-evaluable patients for each cohort (Section 11.1.3.4). All DLT-evaluable patients enrolled during the dose-escalation stage will be evaluated in order to determine the MTD and RP2D.

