11.4.7.2 Dose-limiting Toxicity

Any event that meets the DLT criteria in the opinion of the Investigator should be reported to the Medical Monitor within 24 hours of knowledge of the event. Events will be assessed for DLT criteria according to the CTCAE National Cancer Institute (NCI) v5.0 (Section [8.3.2](#)) except for TLS, which will be assessed for DLT criteria using the Howard modification of Cairo-Bishop criteria ([Appendix G](#)). Toxicity that is clearly and directly related to the underlying malignancy or to an extraneous cause is excluded from the definition of a DLT. A DLT will be defined as the occurrence of any of the following:

- Any CTCAE Grade 3 non-haematological toxicity lasting > 7 days OR any CTCAE Grade 4 non-haematological toxicity, with the exception of:
 - CTCAE Grade 4 nausea, vomiting, or diarrhoea lasting < 7 days in the absence of maximum supportive therapy,
 - Elevation in serum amylase and/or lipase without clinical or radiographic evidence of pancreatitis,
 - CTCAE Grade 3 fatigue, asthenia, fever, anorexia, or constipation.
- Any other cardiac findings of CTCAE Grade ≥ 2 if considered by the Investigator to be clinically significant.
- AZD0466 should be permanently discontinued if a CTCAE Grade ≥ 3 cardiac AE of any duration occurs at any time during study treatment, if considered by the Investigator to be related to study treatment.
- AZD0466 should be permanently discontinued if liver function test abnormalities meets Hy's Law (HL) or Potential Hy's Law (PHL) criteria, and considered by the Investigator to be related to study treatment (see [Appendix E](#)).
- Prolonged myelosuppression: as myelosuppression and cytopenias are expected outcomes of leukaemia treatment, only the criteria defined below will be a DLT:
 - Lack of haematological recovery (ANC remaining $<0.5 \times 10^9/L$, platelets remaining $< 50 \times 10^9/L$) in the absence of active leukaemia in bone marrow (blasts $< 5\%$) and with marrow hypocellularity at $< 5\%$ by Day 42.
- Cairo-Bishop Grade ≥ 3 Clinical TLS ([Appendix G](#)) that occurs despite protocol-recommended management.
- Cairo-Bishop Laboratory TLS ([Appendix G](#)) with metabolic abnormalities that do not resolve within 5 days despite protocol-recommended management.
- Any other toxicity that
 - is greater than at baseline, is clinically significant and/or unacceptable, and is judged to be a DLT by the SRC, or
 - results in a disruption of dosing schedule of more than 21 days.

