Dose-limiting toxicities will not include the following:

- Transient isolated laboratory abnormalities, which are not considered clinically significant and resolve to baseline within 72 hours without any intervention.
- Any documented infection (including COVID-19), bleeding or other direct complication of cytopenia due to active underlying disease.

The DLT evaluation period remains at 35 days for patients with active bone marrow disease by Day 35, irrespective of the blood counts. The DLT evaluation period may be extended to include a repeat bone marrow assessment on Day 42, in the event of myelosuppression (see [Table 6](#)).

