4.14.2 Dose limiting toxicities (DLTs)

A DLT is defined as an AE or abnormal laboratory value that meets the predefined study DLT criteria as described in Section 11.4.7.2 in the study protocol. The DLT evaluation period is defined from first dose of study treatment, up to the end of Cycle 1 (Day 35). DLTs occurring during this period will be used for determination of the maximum tolerated dose (MTD) during Part A in Module 1.

The number of patients evaluable for determination of DLTs and the number of patients with any DLT (and their categorisation) during the DLT evaluation period will be summarised by dose level/cohort, and by SOC and PT, as appropriate.

The listings and tables will be based on the DLT-evaluable analysis set.

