8.5 Analysis Sets

Details of the analysis sets are presented in [Table 5](#).

Table 5 Analysis Sets – Module 1

Population/Analysis set	Description
Screened	All patients that signed the informed consent form (ICF)
Safety	All patients who received at least one dose of AZD0466
Intention-to-treat	All patients who received at least one dose of AZD0466
Evaluable for Response	All patients who have received at least 3 doses of AZD0466 at the target dose level in Cycle 1
DLT-evaluable	
Patients enrolled in the dose-escalation part of Module 1 that have received at least 3 doses of AZD0466 at the target dose level (75% of target doses from Day 8 to Day 29 in Cycle 1) and have completed the safety follow-up through the 35-day DLT evaluation period
 
Or
 
Have experienced a DLT during the 35-day DLT evaluation period in Cycle 1.

Pharmacokinetics	Dosed patients with at least one reportable plasma concentration and no important AEs or protocol deviations that may impact PK

A summary on which analysis set will be used for each outcome variable is provided in [Table 6](#).

Table 6 Summary of outcome variables and analysis sets

Outcome variable	Analysis Set
Study Population/Demography Data	
Disposition	Enrolled
Demography and baseline characteristics	Safety
Important protocol deviations	Safety
Medical History	Safety
Prior/Concomitant Medication	Safety
Safety data	
Exposure	Safety
Adverse Events	Safety
Laboratory measurements	Safety
Vital Signs/ECG/Physical examination	Safety
ECOG PS	Safety
DLTs	DLT-evaluable
Efficacy Data	
CR rate	Evaluable for response; Intention-to-treat
TTR	Evaluable for response
DoR	Evaluable for response
OS	Intention-to-treat
ORR	Evaluable for response; Intention-to-treat
Pharmacokinetics	
Pharmacokinetic variables	PK

CR complete response; DLT dose-limiting toxicity; DoR duration of response; ECOG PS Eastern Co-operative Oncology Group performance status; OS overall survival; PK pharmacokinetic.

The number of enrolled patients included/excluded from each of the analysis sets will be summarized. Patients and data excluded from each analysis set will be listed with the reason for exclusion.

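### The prolonged-myelosuppression DLT has two different marrow criteria in the protocol, and the SAP's 35-day DLT window closes before the Day 42 assessment that both rely on

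*Protocol*

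**What the plan says.** **Criterion.** Protocol 11.4.7.2 says of myelosuppression that "only the criteria defined below will be a DLT". It then requires neutrophils and platelets to remain below 0.5 and 50 × 10⁹/L, blasts below 5%, "and with marrow hypocellularity at $< 5\%$ by Day 42". Protocol 6.6.2, Table 6, has a Cycle 1 row for unrecovered counts with blasts below 5% and cellularity below 10%. Dosing is held at Day 35, and the marrow is repeated at Day 42 if counts have still not recovered. The row then concludes: "Blasts count < 5% and no count recovery this is prolonged myelosuppression and a DLT".

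**Window.** Protocol 11.4.7.2 adds: "The DLT evaluation period may be extended to include a repeat bone marrow assessment on Day 42, in the event of myelosuppression", and refers to Table 6. Protocol 11.4.7.1 defines the second route to DLT-evaluability as "Has experienced a DLT during the 35-day DLT evaluation period in Cycle 1". Protocol Table 21 gives that route with no 35-day limit. SAP 4.14.2 states: "The DLT evaluation period is defined from first dose of study treatment, up to the end of Cycle 1 (Day 35"), and SAP Table 5 repeats the limit: "Have experienced a DLT during the 35-day DLT evaluation period in Cycle 1". Neither SAP section mentions Day 42 or the extension, although 4.14.2 takes its DLT criteria from protocol 11.4.7.2.

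**The concern.** Two sections of the protocol classify the same marrow finding differently. Table 6 cannot be set aside as dosing guidance only: it uses the term DLT, and 11.4.7.2 sends the reader to it for the Day 42 assessment. A site that follows Table 6 would record a DLT that 11.4.7.2 does not recognise.

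The window is a separate fault. Lack of recovery by Day 42 cannot be established by Day 35, so a window ending at Day 35 shuts out this type of DLT under either criterion. Making the cellularity thresholds agree would not repair the SAP table.

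DLT is a Part A primary endpoint, and the SAP tabulates DLTs by dose level on the DLT-evaluable set. A patient whose event is dropped does not leave that table; the patient stays in it as a non-event, which biases the reported rate downward.

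**Working it through.** The plan states no figure on this point, so the check is a comparison of the texts followed by a reading of protocol Table 10.

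**Step 1: the two criteria applied to the same patients.** All have unrecovered counts and blasts below 5%. Cellularity is shown as Day 35 / Day 42.

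| Cellularity | 11.4.7.2 (below 5% by Day 42) | Table 6, below-10% limit still applies at Day 42 | Table 6, limit applies at entry only |
|---|---|---|---|
| 7% / 3% | DLT | DLT | DLT |
| 7% / 7% | not a DLT | DLT | DLT |
| 7% / 15% | not a DLT | not a DLT | DLT |
| 20% / 20% | not a DLT | row not entered | row not entered |

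The sections certainly disagree for row entrants at 5% to under 10% on Day 42. At 10% or more they disagree only if the row's limit is taken to lapse after entry.

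**Step 2: can the patient be evaluable without the DLT?** The first route to evaluability needs 3 of the 4 target doses (Days 8, 15, 22 and 29) and follow-up to Day 35. Protocol 6.6.1 says: "Dose modifications for haematological changes are not allowed in the first 35 days after starting AZD0466 during Cycle 1". Cytopenia alone should therefore not stop the patient from receiving those doses. The patient can enter the denominator by the first route, and the event, classified at Day 42, falls outside the SAP window.

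**Step 3: size in the reported table.** Dropping one DLT among n evaluable patients lowers the observed rate by 1/n:

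- n = 3: 1/3 = 33.3 percentage points.
- n = 6: 1/6 = 16.7 points, for example 2/6 (33.3%) to 1/6 (16.7%).
- n = 12: 1/12 = 8.3 points.

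**Step 4: how sensitive the design was to one DLT (context only).** Table 10 was read for n = 3 to 12, comparing the decision at x DLTs with that at x − 1, for x = 1 to min(n, 7).

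| n | 3 | 4 | 5 | 6 | 7 | 8 | 9 | 10 | 11 | 12 | Total |
|---|---|---|---|---|---|---|---|---|---|---|---|
| Steps | 3 | 4 | 5 | 6 | 7 | 7 | 7 | 7 | 7 | 7 | 60 |
| Decision changes | 3 | 3 | 2 | 3 | 3 | 3 | 3 | 3 | 3 | 2 | 28 |

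Ten of the 28 changes, one for each n, end in escalation. Examples are 1/3 (stay) to 0/3 (escalate), 2/6 (stay) to 1/6 (escalate), and 2/5 (de-escalate) to 1/5 (escalate). The other 32 steps leave the decision unchanged, for example 1/6 to 0/6. The steps are weighted equally, so 28/60 is a count of table cells and not a probability.

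**The case against.** The case on the other side has five parts.

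1. **There is a default criterion.** Core Section 6.7 and SAP 4.14.2 both point to 11.4.7, and 11.4.7.2 declares itself exclusive. This stands for analysis. It does not undo a DLT that a site recorded under Table 6.

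2. **The cytopenia is already present at Day 35.** If the DLT is dated by onset, it falls inside the window and the Day 42 marrow only confirms it. That is a workable rule, but neither document states it. A programmer following SAP 4.14.2 and Table 5 literally would exclude an event classified at Day 42.

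3. **The protocol is not uniformly at 35 days.** Table 21 has no such limit and 11.4.7.2 allows the extension. This is correct, and it shows that the SAP adopted the narrower of the protocol's own versions.

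4. **The event would appear elsewhere.** The adverse event overview in SAP 4.14.4 counts events classed as DLTs on the safety set, up to 28 days after discontinuation. With a last Cycle 1 dose on Day 29 that reaches 29 + 28 = Day 57. The event would thus be visible by dose level. The overview and the DLT table could then disagree about the same patient with no explanation.

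5. **The effect on conduct is past.** Recruitment stopped in June 2023, and SAP 4.14.3 excludes the MTD evaluation. This stands, and it is why the Table 10 count is context only. It leaves the reported DLT counts unresolved.

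**Conclusion.** The concern holds. The protocol gives two criteria for the same DLT, and they certainly disagree for Table 6 row entrants with Day 42 cellularity of 5% to under 10%. Independently, the SAP window as written omits the Day 42 assessment on which both criteria depend. A patient with this DLT can be counted as evaluable and event-free.

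The window conclusion assumes that the DLT is dated when its criterion is met, since no onset-dating rule is given. It also assumes that the patient received at least 3 target doses and was followed to Day 35.

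The consequence is confined to reported DLT counts by dose level: 1/n per affected patient, or 33.3 percentage points at n = 3 down to 8.3 at n = 12. The documents do not show how many patients, if any, are affected. The point should be fixed because it can misstate a Part A primary endpoint and the correction is small. It no longer bears on dose escalation.

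**What to change.** 1. Use one Day 42 criterion with one cellularity threshold. Take 11.4.7.2 as the default for analysis unless the sponsor and the SRC decide otherwise and document it. If the protocol is amended, word Table 6 and 11.4.7.2 identically.
2. In SAP 4.14.2 and in the DLT-evaluable definition in SAP Table 5, extend the window to include the Day 42 myelosuppression assessment. Make the same change in protocol 11.4.7.1 if the protocol is amended.
3. In the report, flag every patient whose DLT status differs between the two criteria or who was first classified at Day 42. Give DLT counts by dose level both ways, and reconcile them with the DLT row in the adverse event overview.

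The cost is one sentence in each of the two SAP sections, one report footnote, and a re-check of patients who had a Day 42 marrow. No new data are needed.

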6.6.2 Retreatment Criteria

Administration of AZD0466 in subsequent cycles will be guided by presence of measurable disease and adequate haematopoiesis, as described below.

Criteria for holding administration of AZD0466

The haematological criteria for withholding AZD0466 are as follows (Table 6):

- 1 **Inadequate haematopoiesis** as demonstrated by lack of peripheral blood count recovery [absolute neutrophil count (ANC) $< 0.5 \times 10^9/L$, and platelet count $< 50 \times 10^9/L$] in the absence of active bone marrow leukaemia (marrow blasts $< 5\%$).
 - Some patients with low blood counts (ANC $< 0.5 \times 10^9/L$ and platelet count $< 50 \times 10^9/L$) may have an aplastic or hypoplastic marrow ($< 10\%$ cellularity on bone marrow core biopsy). In patients with an aplastic or hypoplastic marrow and high leukaemic burden (eg, 5% cellularity and 95% leukaemic blasts), or if the Investigator determines the hypocellularity is attributable to residual leukaemia and not AZD0466, continued administration of AZD0466 may be permitted after discussion with the Medical Monitor.
 - If AZD0466 is withheld due to cytopenias and bone marrow aplasia/hypoplasia ($< 10\%$ cellularity on core bone marrow core biopsy) in the absence of leukaemia (eg, 5% leukaemic blasts), the patient should be closely monitored for blood count recovery and a repeat bone marrow assessment should be considered at weekly intervals.
- 2 **Progressive disease** (Appendix J and Appendix K): permanently discontinue AZD0466 in the absence of clinical benefit after discussion with the Medical Monitor.

Criteria for administration/continuation of AZD0466

The next cycle of AZD0466 can proceed without delay if ANC $> 0.5 \times 10^9/L$ and platelets $> 50 \times 10^9/L$ (without platelet or growth factor support). For patients without peripheral blood count recovery, the next cycle can start if there is active leukaemia with 5% or higher blasts in the bone marrow.

Table 6 Treatment Criteria Based on Bone Marrow, ANC and Transfusion Independent Platelet Count in the Absence of Peripheral Blasts

Event	ANC ($10^9/L$)	Platelets ($10^9/L$)	Bone marrow	Action
Cycle 1	> 0.5	> 50	-	
 Evaluate bone marrow disease but continue to next cycle irrespective of percentage of blasts (unless determined to have rapidly progressive disease and taken off study)

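### Table 6 and Section 11.4.7.2 apply different marrow cellularity conditions to prolonged myelosuppression, so the same Part A patient can be a DLT under one and not under the other

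*Protocol*

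**What the plan says.** Two current sections of the protocol classify prolonged myelosuppression.

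- **Section 6.6.2, Table 6, Cycle 1.** The relevant row applies to patients with ANC < 0.5 × 10⁹/L, platelets < 50 × 10⁹/L, marrow blasts < 5% and cellularity < 10%. Drug is held at Day 35. The next instruction is "If no recovery, repeat bone marrow at Day 42". If the Day 42 marrow shows blasts below 5% and counts have still not recovered, the table says "this is prolonged myelosuppression and a DLT".
- **Section 11.4.7.2.** For myelosuppression, "only the criteria defined below will be a DLT". The criterion uses the same ANC, platelet and blast limits, but adds "and with marrow hypocellularity at" below 5% by Day 42.

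Other text bears on which rule applies:

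- Section 6.7 refers the reader to Section 11.4.7 for DLTs, and SAP Section 4.14.2 takes the DLT criteria from Section 11.4.7.2.
- Section 11.4.7.2 itself sends the reader to Table 6 when it says that the evaluation period "may be extended to include a repeat bone marrow assessment on Day 42, in the event of myelosuppression".
- Section 6.6.2 uses cellularity below 10% when it describes patients who "may have an aplastic or hypoplastic marrow".

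**The concern.** The two rules agree on counts and blasts but not on cellularity. Table 6 does more than give dosing advice: it labels the event a DLT. A site working from Table 6 at the Day 42 visit would report a DLT that 11.4.7.2 excludes.

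The DLT count at each dose level is the input to the mTPI-2 decision table (Section 11.1.3.3, Table 10) and to the isotonic regression for the MTD (Section 11.4.7.3). Cohorts can be as small as 3 evaluable patients, so one reclassified patient can change the recommendation given to the Safety Review Committee (SRC). Section 6.6.1 says myelosuppression is expected in this population, so the criterion can be expected to come into use.

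**Working it through.** **Step 1. Apply both rules to the same patient.** Take a Part A patient at Day 42 with ANC < 0.5, platelets < 50 and blasts < 5%, who entered the Table 6 row at cellularity < 10%. Vary only the Day 42 cellularity.

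| Day 42 cellularity | Table 6 | Section 11.4.7.2 |
|---|---|---|
| 2% | DLT | DLT |
| 4% | DLT | DLT |
| 5% | DLT | not a DLT |
| 7% | DLT | not a DLT |
| 9% | DLT | not a DLT |

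If the row-entry condition is read as still applying at Day 42, the rules disagree from 5% to below 10%. The Day 42 line does not re-check cellularity. Read literally, the disagreement therefore has no upper limit for a patient whose marrow has begun to refill without count recovery.

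**Step 2. Effect of one extra DLT on the printed Table 10.** Decisions are E (escalate), S (stay), D (de-escalate) and DNT (dose not tolerated). For each n from 3 to 12, compare the printed decision at k and k + 1 DLTs, for k + 1 up to n or 7, whichever is smaller.

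| n | Pairs that change / pairs | Changes |
|---|---|---|
| 3 | 3/3 | 0→1 E to S; 1→2 S to D; 2→3 D to DNT |
| 4 | 3/4 | 0→1 E to S; 1→2 S to D; 2→3 D to DNT |
| 5 | 2/5 | 1→2 E to D; 3→4 D to DNT |
| 6 | 3/6 | 1→2 E to S; 2→3 S to D; 3→4 D to DNT |
| 7 | 3/7 | 1→2 E to S; 2→3 S to D; 4→5 D to DNT |
| 8, 9 | 3/7 each | 2→3 E to S; 3→4 S to D; 4→5 D to DNT |
| 10, 11 | 3/7 each | 2→3 E to S; 3→4 S to D; 5→6 D to DNT |
| 12 | 2/7 | 3→4 E to D; 6→7 D to DNT |

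Changing pairs: 3 + 3 + 2 + 3 + (5 × 3) + 2 = 28. All pairs: 3 + 4 + 5 + 6 + (6 × 7) = 60. The result is 28 of 60. Some pairs do not change; for example, 0/6 and 1/6 are both E.

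**Step 3. Probability that one ambiguous patient changes the recommendation.** Assume the other n − 1 patients have independent DLTs at rate p. The documents give no rate, so p = 0.1, 0.2 and 0.3 are assumptions. Then

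P(change) = Σ over the changing k of C(n − 1, k) pᵏ (1 − p)ⁿ⁻¹⁻ᵏ.

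- n = 3: every k from 0 to 2 changes, so P = 1.00 at all three rates.
- n = 6 (k = 1, 2, 3 among 5 others): at p = 0.1, 0.328 + 0.073 + 0.008 = 0.409; at p = 0.2, 0.410 + 0.205 + 0.051 = 0.666; at p = 0.3, 0.360 + 0.309 + 0.132 = 0.801.
- n = 12 (k = 3, 6 among 11 others): 0.071, 0.231 and 0.313.

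These figures hold n fixed. That is reasonable where the patient received at least 3 target doses and so is DLT-evaluable under either rule (Section 11.4.7.1). Section 6.6.1 bars dose modification for haematological changes in the first 35 days, which makes this the natural case.

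**The case against.** The strongest reply is that the documents already show which text governs. Section 6.7 refers DLTs to Section 11.4.7, 11.4.7.2 is worded as an exclusive definition, and the SAP cites 11.4.7.2 and not Table 6. Table 6 is a table of treatment criteria. On this view, the reference from 11.4.7.2 to Table 6 concerns only the timing of the repeat marrow, and the 10% cut-off only describes a hypoplastic marrow for withholding drug. This carries weight: a careful reader would probably choose 11.4.7.2. But Table 6 expressly assigns DLT status, the DLT section leads the reader there for this same assessment, and no precedence is stated.

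Second, suspected DLTs go to the Medical Monitor, and the SRC weighs all available data alongside the mTPI-2 recommendation. It may also judge other toxicities to be DLTs. This is partial mitigation. That provision is discretionary, and the exclusive wording argues against using it for myelosuppression. The alternative limb, a dosing disruption of more than 21 days, is not met at Day 42: Cycle 1 lasts 35 days, so the next dose is due about Day 36 and the delay is about 6 days.

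Third, the sizes above describe any single extra DLT and depend on an ambiguous patient existing. That is correct.

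Fourth, the effect on the final analysis is limited. SAP Section 1 records that recruitment stopped and the study was terminated. SAP Section 4.14.3 excludes the MTD evaluation. SAP Section 4.14.2 ends the DLT period at Day 35, so a Day 42 DLT might fall outside the summary under either wording. That also stands, and it places the consequence mainly in the dose-escalation decisions. The SAP does still tabulate DLTs and AEs classified as DLTs (Sections 4.14.2 and 4.14.4).

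**Conclusion.** The concern holds: the protocol contains two incompatible rules for the same event. They disagree for Part A Cycle 1 patients with no count recovery, blasts below 5% and Day 42 cellularity of 5% or more. Table 6 does have a cellularity condition, below 10% at row entry; what it lacks is the 5% condition.

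Given one such patient, the Table 10 recommendation changes with certainty at n = 3. At assumed DLT rates of 10%, 20% and 30% in the other patients, it changes with probability 41%, 67% and 80% at n = 6, and 7%, 23% and 31% at n = 12. No unconditional effect on dose selection can be given, because the documents give no frequency for this group. The pointers to 11.4.7.2 and the SRC's review reduce the risk but do not remove it. The definition of a primary endpoint that drives dose escalation should not depend on which section a site reads.

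**What to change.** Choose one Day 42 cellularity threshold; this is a clinical decision, and nothing here favours 5% over 10%. State it identically in Section 11.4.7.2 and in the Day 42 line of Table 6. Add one sentence saying that 11.4.7.2 governs DLT classification and Table 6 governs dosing. The rules then agree at every cellularity value.

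The cost is protocol wording only. The Day 42 marrow is already specified, so no procedure is added, and the SAP already cites 11.4.7.2 and needs no change on this point. Because recruitment has stopped, the change cannot alter past escalation decisions; it would settle which rule the reported DLTs follow.
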